7.1.2 Unsolicited Adverse Events

Unsolicited adverse events are defined as any adverse events occurring within the 7-day window following vaccination and not specifically solicited in the diary, or any adverse event that occurs outside the 7-day diary solicitation period. All unsolicited AEs of any severity will be collected from the time of first study vaccination through Day 70 (ie, until 14 days after the second vaccination). Any relevant observations made prior to the first dose of study vaccine are to be recorded on the AE eCRF but will not be considered TEAEs and will be reported separately from TEAEs. The time periods for summary of adverse events are described at the end of this section. Summaries for other time periods may also be produced.

Unsolicited AEs will be coded by Preferred term (PT) and System Organ Class (SOC) using the latest version of Medical Dictionary of Regulatory Activities (MedDRA). Unsolicited AEs will be summarized overall and by study vaccine group then by SOC/PT as well as by severity (Mild, Moderate, Severe, or Potentially Life Threatening), and relatedness (not related,

related, not applicable) to the study vaccine. For multiple occurrences of an AE in the same participant, a participant will be counted only once, using the most severe or most related occurrence for the summarization by severity or relationship to the study vaccine, respectively. The number and percentage with its corresponding exact 95% CIs of unsolicited AEs will be calculated using Clopper-Pearson method.

An MAAE is defined as an AE that leads to an unscheduled visit to a healthcare practitioner. AESIs include PIMMCs, AEs specific to complications of COVID-19 (listed in [Error!](#)

[Reference source not found.](#)), or other potential AEs that may be determined at any time by regulatory authorities as additional information concerning COVID-19 is obtained. All MAAEs and AESIs (including PIMMCs and complications to COVID-19) will be collected from the first study vaccination through Day 182 after first vaccination. An AESI must be reported as if it is an SAE. SAE is defined as an event considered “serious” if, in the view of either the Investigator or Sponsor, it results in any of the outcomes listed in Section 8.1 Protocol. All SAEs will be collected from signing of informed consent until completion of the EoS.

All MAAEs, any MAAEs related to vaccine, AESIs (including PIMMCs and complications to COVID-19), SAEs, any SAEs related to vaccine through Day 182 after first vaccination will be summarized overall and by the study vaccine group as well as by severity using the provided criteria ([Appendix 2](#) and [Appendix 3](#)).

The following summaries of unsolicited AEs will be presented overall and by the study vaccine group as part of the primary analysis of safety:

- Overall summary of all unsolicited AEs (Days 0 - 70)
- Summaries of all unsolicited AEs by MedDRA SOC/PT and severity (Days 0 - 70)
- Summaries of all unsolicited AEs by MedDRA SOC/PT and relationship to study vaccine (Days 0 - 70)
- Summaries of MAAEs, SAEs, and AESIs (including PIMMCs and complications to COVID-19) by MedDRA SOC/PT and relationship to study vaccine (Days 0-70, Days 71-182, Days 0 - 182)
- Listings of all unsolicited AEs including MAAEs, AESIs (including PIMMCs and complications to COVID-19) and SAEs (Days 0-70, Days 71-182, Days 0 - 182)

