Interventions	
Each participant will receive 2 injections, the first dose on Day 0 and the second dose on Day 56 in the same deltoid (except for participants in Vaccine Group O who will receive a third injection at Day 70). Treatments will comprise 1 of 16 regimens of investigational vaccines delivering either:
 

• One of 14 formulations of an ICC vaccine (comprising 12 unique formulations and 2 pairs of duplicate formulations) containing 1 of 4 dose levels of influenza HA protein (5, 10, 35, or 60 µg) and 1 of 3 dose levels of SARS-CoV-2 rS protein (2.5, 7.5, or 22.5 µg) with Matrix-M1 adjuvant (50 µg); in a two-dose regimen (Vaccine Groups A-N); OR

• A reference formulation of SARS-CoV-2 rS (5 µg) nanoparticle vaccine with Matrix-M1 adjuvant (50 µg), in a two-dose regimen (Vaccine Group P); OR

• A reference formulation of qNIV (60 µg HA per strain) vaccine with Matrix-M1 adjuvant (75 µg), followed by a reference formulation of SARS-CoV-2 rS (5 µg) nanoparticle vaccine with Matrix-M1 adjuvant, in a two-dose regimen, (Vaccine Group O).

 
The antigens and adjuvant dose values in the Study Design Table are nominal and reflect target doses. The qNIV antigen, SARS-CoV-2 rS antigen, and Matrix-M1 adjuvant will each be available in separate drug product vials and will be mixed in the clinic prior to administration to achieve the target doses of ICC, qNIV with Matrix-M1 adjuvant, or SARS-CoV-2 rS with Matrix-M1 adjuvant (actual doses will be within <math>\pm</math> 10% to 20% of intended target doses). Details of the final product mixing schemes to be implemented by the site pharmacist or designee, the actual content of doses achieved by the in-clinic mixing of drug product lots, and injected volumes used are provided in the Pharmacy Manual.
 
For all doses of test article, the assigned vaccine will be administered by IM injection in an approximate total volume of 0.3 to 1.0 mL.

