### 3 OBJECTIVES AND ENDPOINTS

The purpose of this study is to evaluate the safety and immunogenicity of multiple formulations of ICC vaccines in older adults. As a primary objective, the study is designed to examine the hypothesis that ICC investigational vaccines will have comparable safety and tolerability profiles to those of the reference formulations.

Study participants in Vaccine Groups A through P will receive 2 injections of vaccine, the first dose on Day 0 and the second dose on Day 56; participants in Vaccine Group O will receive an additional IM dose of 5 µg SARS CoV-2 rS with 50 µg Matrix-M1 adjuvant on Day 70 to ensure this group received 2 doses of COVID-19 vaccine. A total of 14 formulations of ICC vaccine (comprising 12 unique formulations and 2 pairs of duplicated formulations) and 2 reference vaccines, will be administered in this study.

The primary goal of this study is to identify one or more optimal dose levels of HA and rS antigens administered as a combination vaccine, which minimize both antigen doses and manage any immunologic interference, using a DoE modeling approach. An overview of all study objectives and endpoints in provided in

Table 2 Study 2019nCoV-E-101: Primary, Secondary, and Exploratory Objectives and Endpoints

Tier	Objectives	Endpoints
Primary Safety	To describe the tolerability and safety profiles associated with the receipt of the multiple vaccine formulations/regimens included in the study. Safety profiles will include: 

Solicited AEs over 7 days after each of the first and second doses (including immediate AEs in the 30 minutes after dosing), to encompass both local injection site symptoms/signs and systemic symptoms/signs.

Unsolicited AEs over 70 days after the first dose.

MAAEs, SAEs, and AESIs over 6 months (approximately 182 days) after first dose.

	

Numbers and percentages (with 95% CIs) of participants with solicited local and systemic AEs over the 7 days post-injection after first and second doses.

Proportions of participants reporting all AEs, solicited and unsolicited over 70 days after first dose.

Proportions of participants with MAAEs, SAEs, and AESIs will be collected for 6 months after the first dose.

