#### 7.1.1.2 Dosing and Administration

The qNIV antigen will be mixed with Matrix-M1 adjuvant in the clinic pharmacy, or an area designated for this function, according to the Pharmacy Manual on the day of administration by a qualified member of the study site personnel. The vaccine should be administered according to standard aseptic practice by qualified study site personnel in a way so as to maintain the blind, as directed in the Pharmacy Manual.

Following in-clinic mixing according to the Pharmacy Manual, the qNIV with Matrix-M1 vaccine can be stored at room temperature, in a secured location, for up to 3 hours in the mixing vial or 1 hour in the final administration syringe. DO NOT FREEZE or REFRIGERATE once mixed.

The qNIV with Matrix-M1 adjuvant vaccine regimen will comprise one IM injection (Day 0 for Vaccine Group O) (Table 3, Table 4).

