#### 7.1.2.2 Dosing and Administration

The SARS-CoV-2 rS antigen will be mixed with Matrix-M1 adjuvant in the clinic pharmacy, or an area designated for this function, according to the Pharmacy Manual on the day of administration by a qualified member of study site personnel. The vaccine should be administered according to standard aseptic practice by qualified study site personnel in a way so as to maintain the blind, as directed in the Pharmacy Manual.

Following in-clinic mixing according to the Pharmacy Manual, the SARS-CoV-2 rS with Matrix-M1 vaccine can be stored at room temperature, in a secured location, for up to 3 hours in the mixing vial or 1 hour in the final administration syringe. DO NOT FREEZE or REFRIGERATE once mixed.

The SARS-CoV-2 rS with Matrix-M1 adjuvant vaccine regimen will comprise 2 identical IM injections (Day 0 and Day 56 for Group P; and Day 56 and Day 70 for Group O) ([Table 3](#); [Table 4](#)).

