- Duration of all local (injection site)/systemic reactogenicity AEs for the first dosing/the second dosing
- Listings of participants with local (injection site)/systemic reactogenicity AEs
- Summaries of participants with local/systemic solicited AEs continuing past Day 6

In addition, between-group difference of proportions of participants experiencing any solicited local (injection site)/systemic AE between groups will be calculated as follows:

- Groups A to N individually after first dose against Groups O and P after first dose
- Groups A to N individually across 2 doses against Groups O and P after first dose
- Groups A to N individually across 2 doses against Group P across 2 doses

Two-sided 95% CIs for the risk differences will be calculated with the method of Miettinen and Nurminen. Sample SAS code is presented below:

```
proc freq data=<solicited_data>;
  tables <arm>*<indicator of occurrence> / missing riskdiff (cl=MN);
run;
```

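### No committed unsolicited-AE, MAAE, SAE or AESI table is cut at the second dose, so the safety tables give no qNIV-only reference period for Group O

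*SAP*

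**What the plan says.** **Group O's regimen.** Protocol 7.1.1.2 states: "The qNIV with Matrix-M1 adjuvant vaccine regimen will comprise one IM injection (Day 0 for Vaccine Group O". Protocol 7.1.2.2 gives the rS injection days as "Day 0 and Day 56 for Group P; and Day 56 and Day 70 for Group O". Protocol Table 3 and SAP Table 1 agree: 60 µg HA per strain with 75 µg Matrix-M1 on Day 0, then 5 µg rS with 50 µg Matrix-M1 and no HA on Day 56. The Synopsis describes the group as qNIV "followed by a reference formulation of SARS-CoV-2 rS (5 µg) nanoparticle vaccine with Matrix-M1 adjuvant, in a two-dose regimen, (Vaccine Group O". The dosing tables nevertheless place it under the qNIV reference heading.

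**Unsolicited events.** SAP 7.1.2 lists an "Overall summary of all unsolicited AEs (Days 0 - 70", with breakdowns by SOC/PT, severity and relatedness over the same window. MAAEs, SAEs and AESIs are cut at Days 0-70, 71-182 and 0-182. Protocol 9.3.6.2 likewise summarises unsolicited AEs through Day 70. On other cuts, SAP 7.1.2 says only: "Summaries for other time periods may also be produced".

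**Solicited events and HAI.** SAP 7.1.1 reports solicited AEs by dose. In its between-group risk differences, Group O appears only after its first dose, and the two-dose contrast is "Groups A to N individually across 2 doses against Group P across 2 doses". SAP 7.2.1 compares Groups A-N at Day 28 and at Day 70 with Group O at Day 28 only.

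**Purpose.** Protocol Section 3 sets out the hypothesis that "ICC investigational vaccines will have comparable safety and tolerability profiles to those of the reference formulations".

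**The concern.** The product and the adjuvant dose in Group O both change at the second injection, and no committed unsolicited-event table breaks there. Someone checking the safety hypothesis will naturally set the A-N columns beside the group headed as the qNIV reference. Over Days 0-70 that column includes participants whose only event followed rS. The relatedness tables do not help, because they classify relation to study vaccine without saying which injection.

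At stake is a clean descriptive answer to one question: after a single injection, how do unsolicited events with the combination compare with those after qNIV alone? The SAP takes care over this for solicited AEs and HAI, but does not carry the same care into SAP 7.1.2.

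**Working it through.** No figure in the plan is disputed. The nearest stated figure is the 87% chance of seeing at least one AE of 5% incidence with 40 per group (Protocol 9.2.1, SAP 1.2). It reproduces: 1 − 0.95^40 = 0.8715.

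**Step 1. Where the cuts fall against the injections in Group O**

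| Output | Periods committed | Break at second dose? |
|---|---|---|
| Solicited AEs (SAP 7.1.1) | each dose, and both initial doses together | yes |
| Solicited risk differences (SAP 7.1.1) | Group O after first dose only | yes |
| HAI ratios (SAP 7.2.1) | Group O at Day 28 only | yes |
| Unsolicited AEs (SAP 7.1.2) | Days 0-70 | no |
| MAAEs, SAEs, AESIs (SAP 7.1.2) | Days 0-70, 71-182, 0-182 | no |

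**Step 2. Share of the block that follows rS.** Days 0 to 70 inclusive are 71 days. Days 0-55 (56 days) follow qNIV alone. Days 56-70 (15 days) include and follow rS. 15/71 = 21%. If the second dose is given on Day 61, the end of the protocol's +5-day window, and the block closes at calendar Day 70, the share is 10/71 = 14%. This is why the split should use the actual dose date.

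**Step 3. Direction.** Let p be the probability of at least one unsolicited AE before the second dose, and q the probability of at least one from the second dose through Day 70. If the two are independent, the Day 0-70 proportion is 1 − (1 − p)(1 − q), and its excess over p is q(1 − p). This is never negative. Independence affects the size of the excess but not its direction, because a longer window can only add participants.

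**Step 4. Size, as illustration only.** The documents give neither p nor q for this trial. As an anchor for p, take the 18% of qNIV recipients with unsolicited AEs in the sponsor's Phase 2 qNIV study (Protocol 2.1.5.1.1). Those adults were 65 or older, and the summary does not state the counting period. For q, assume 5% to 20%, a range not in the documents.

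- q = 5%: 1 − 0.82 × 0.95 = 22.1%, an excess of 4.1 points.
- q = 20%: 1 − 0.82 × 0.80 = 34.4%, an excess of 16.4 points.
- With p from 10% to 30% and the same q, the excess runs from 0.05 × 0.70 = 3.5 points to 0.20 × 0.90 = 18 points.

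**Step 5. Against sampling error.** With 40 per group, one participant is 1/40 = 2.5 points. The exact 95% interval is about 7% to 33% for 7/40 and about 15% to 44% for 11/40. A shift of 4 to 16 points would not stand out from chance in one group, but its direction is known in advance if the column is read as qNIV alone.

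**The case against.** The case for leaving the plan alone is substantial, and most of it stands.

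- **The column is correct for what it is.** Group O is defined as a sequence, and SAP 7.1.1 itself summarises solicited AEs across both initial doses with Group O included. The SAP never calls the Day 0-70 column qNIV-only.
- **Days 0-70 is the protocol's endpoint.** SAP 7.1.2 implements it faithfully. A split adds to it and does not correct it.
- **Nothing formal depends on the column.** Protocol 9.1 disclaims formal hypotheses, no between-group contrast of unsolicited AEs is specified, and formulation selection rests on immunogenicity modelling. The explicit benchmarking role of the reference groups is stated for immune responses.

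A reader might go further and infer that Group O cannot serve as a safety benchmark, or that first-dose and second-dose events cannot be told apart. The documents do not support either. AE start dates and causality are recorded (Protocol 8.2), dosing dates are recorded (Protocol 7.3), listings are committed, other periods are allowed, and Group P receives rS throughout. A reader might also argue that half of the relevant time follows the wrong product, by assuming that events cluster in the 14 days after each injection. No section supports that clustering, and it counts days, not events.

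What the objection does not answer is the permissive wording. An optional summary names no second-dose cut. SAP 1.4 unblinds the sponsor's biostatistics team at the Day 70 analysis, so an optional period could be chosen with results in view.

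**Conclusion.** The narrow point holds, as a cheap improvement. The pre-specified tables for unsolicited AEs, MAAEs, SAEs and AESIs give no qNIV-only reference for the comparable-safety hypothesis, and Group O's Day 0-70 column is a sequential-regimen rate. About 21% of that block, by nominal calendar days, falls on or after rS. The column can only lie at or above the qNIV-only rate. The amount is not fixed by the documents, and the 4 to 16 points above rest on an assumed post-rS rate, a borrowed anchor and independence.

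The point takes Group O's regimen from Protocol Table 3, Protocol 7.1.1.2 and 7.1.2.2, and SAP Table 1. Protocol Table 4 instead lists the qNIV reference as two doses, on Days 0 and 56; these passages must be reconciled. On the Table 3 schedule no group receives a second qNIV injection, so no cut of the data can supply a two-dose qNIV reference.

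**What to change.** In SAP 7.1.2:

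1. Pre-specify two added periods for all groups, for unsolicited AEs, MAAEs, SAEs and AESIs: first dose to immediately before the actual second dose, and actual second dose through Day 70.
2. Use Group O's first period as the qNIV reference, beside the first period of Groups A-N, so that both sides cover one injection. Read Group O's second period as rS after qNIV.
3. Keep the Day 0-70 table as the protocol endpoint, with a footnote that Group O is qNIV followed by rS.
4. State how events on a dosing day are assigned, in particular Group O events on Day 70, its third-dose day. Protocol 8.2 lists a start date but no start time for AEs.
5. State how partial onset dates are placed in a period. The rule in SAP 11.5 is anchored to the Day 0 vaccination and was not written for a second-dose split.
6. Reconcile the second-dose window, which is +5 days in the protocol and in the SAP's schedule of events but ±4 days in SAP 1.1 and SAP Table 1.

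No new data are needed, because onset and dosing dates are already collected. The cost is more tables, with smaller counts in each period.

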#### 6.1.1.3 Day 56 - Second Study Vaccination (+ 5 Days)

All participants with confirmed eligibility will have the following procedures performed prior to the second study vaccination:

- Prior and concomitant medications, including recent and current medications to be reviewed to ensure eligibility criteria are fulfilled (see definitions in Section 0).
- Vital signs measurements, including respiratory rate, blood pressure, pulse rate, pulse oximetry, and temperature (oral or via forehead/ear reader).
- Urine pregnancy test for women of childbearing potential only. A urine pregnancy test will be performed prior to each study vaccination. A positive urine pregnancy test at any time will result in the participant not receiving any further study vaccination.
- Symptom-directed (targeted) physical examination.
- Blood sampling for SARS-CoV-2 immunogenicity (ELISA for anti-rS-protein serology), HAI serology, and influenza virus MN50 assay.
- Blood sampling for SARS-CoV-2 MN50 assay.
- Assessment of unsolicited AEs, MAAEs, SAEs, and AESIs (including PIMMC).

At the time of second study vaccination, the following procedures will be conducted for all randomly assigned participants:

- Alcohol swab cleansing of the injection sites for study vaccine administration
- Vaccination with study vaccine as an IM injection.
- Monitoring for reactogenicity; participants will remain in clinic for at least 30 minutes to be monitored for any severe reactogenicity. Severe reactions will be noted as AEs on day of study vaccination.

Following vaccination, participants will utilize an eDiary to record reactogenicity. All participants will record reactogenicity on the day of vaccination and for an additional 6 days after vaccination (ie, Day 56 through Day 62, inclusive). Study site personnel will regularly review the eDiary for completeness. Should any reactogenicity event extend beyond 6 days after vaccination (toxicity grade  $\geq 1$ ), then it will be recorded as an AE with start dates of Day 63 (the first day after completion of the participant solicited symptom eDiary) and followed to resolution per ICH guidelines for dataset capture. The toxicology grading scale implemented in the electronic diary for the study is included in [Appendix 2 \(Table 7\)](#).

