### 6.1.3 End of Study

#### 6.1.3.1 Day 182 – EoS Visit ( $\pm$ 14 Days)

During this EoS visit, the following procedures will be performed:

- Prior and concomitant medications (only concomitant medications taken for any MAAEs, SAEs, or AESIs (including PIMMCs) will be recorded) (see definitions in Section 0).
- Vital signs measurements, including respiratory rate, blood pressure, pulse rate, pulse oximetry, and temperature (oral or via forehead/ear reader).
- Symptom-directed (targeted) physical examination.
- Blood sampling for SARS-CoV-2 (anti-NP) antibodies.
- Blood sampling for SARS-CoV-2 (ELISA for anti-rS-protein serology), HAI serology, and influenza virus MN50 assay (testing performed by Novavax).
- Blood sampling for SARS-CoV-2 MN50 assay.
- Assessment of MAAEs, SAEs, and AESIs (including PIMMC).
- CMI Subset Participants ONLY: Blood sampling for CMI (as measured by ICCS and/or ELISpot) assay for cytokines IL-2, TNF $\alpha$ , CD40L, and IFN $\gamma$ .
- Completion of the EoS form.

Also, at the EoS visit, it should be confirmed that no pregnancy has occurred in women of childbearing potential since the last contact.

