### 8.2.2 Time Frame for Collection

All AEs reported or observed during the study will be recorded on the AE page of the eCRF.

Medical occurrences that begin prior to the first dose of study vaccine will be recorded on the Medical History/Current Medical Conditions section of the eCRF not the AE section.

All unsolicited AEs of any severity will be collected from the time of first study vaccination through Day 70 (ie, until 14 days after the second vaccination). Any relevant observations made prior to the first dose of study vaccine are to be recorded on the AE eCRF but will not be considered TEAEs and will be reported separately from TEAEs.

MAAEs and AESIs (including PIMMCs) will be collected from the time of first study vaccination until EoS.

All SAEs will be collected from signing of informed consent until completion of the EoS.

Participants who receive an approved/authorized vaccine (see Section 7.2.4.1), will be encouraged to remain in the study for safety follow-up and safety assessments will be performed via the timelines and mechanisms as described herein. In addition, all vaccine administration errors, AEs, SAEs, cases of multisystem inflammatory syndrome, and hospitalized or fatal cases

of COVID-19 following vaccination with the approved/authorized must be reported following local regulatory reporting guidance for safety events that occur in subjects who receive approved/authorized vaccines within the study.

At any time after completion of the EoS visit, if an investigator learns of an SAE that could reasonably be considered related to study vaccine, they should promptly notify the Sponsor.

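### The planned SAE, MAAE and AESI tables end at Day 182 although collection runs to an end-of-study visit as late as Day 196, and Day 70 is 14 days after dose 2 only when dose 2 falls on Day 56

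*SAP*

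**What the plan says.** **Tabulation.** SAP 7.1.2 summarises MAAEs, SAEs and AESIs by "relationship to study vaccine (Days 0-70, Days 71-182, Days 0 - 182"). Its listings stop at the same point: "COVID-19) and SAEs (Days 0-70, Days 71-182, Days 0 - 182"). Ordinary unsolicited AEs get tables for the first period only, such as "Overall summary of all unsolicited AEs (Days 0 - 70"). Protocol 9.3.1 and 9.3.6.2 also stop at Day 182.

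**Collection.** For SAEs, SAP 7.1.2 states "All SAEs will be collected from signing of informed consent until completion of the EoS", and Protocol 8.2.2 agrees. For the other two classes Protocol 8.2.2 states "MAAEs and AESIs (including PIMMCs) will be collected from the time of first study vaccination until EoS", whereas SAP 7.1.2 ends their collection at Day 182. Protocol 9.3.6.2 describes collection of all three classes as ending at Day 182. The EoS visit has a window of ±14 days and includes "Assessment of MAAEs, SAEs, and AESIs (including PIMMC") (Protocol 6.1.3.1).

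**Day 70.** Protocol 8.2.2 collects unsolicited AEs "through Day 70 (ie, until 14 days after the second vaccination"), and SAP 7.1.2 repeats this. The second dose has a window: "Day 56 - Second Study Vaccination (+ 5 Days"). The Day 70 visit also has a +5-day window. Footnote 5 of the schedule of events allows a delay of up to 7 days in the second dose. SAP 1.1 and SAP Table 1 give the dose 2 window as ±4 days instead.

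**The concern.** Collection follows the participant to an actual visit, while tabulation stops at a fixed day number. An SAE found at an in-window EoS visit on, say, Day 190 is collected as planned, yet no planned summary has a place for it. SAE, MAAE and AESI proportions are primary safety endpoints, and in arms of 40 one participant is 2.5%. If the plan does not say where such an event goes, the choice falls to whoever programs the tables, after the sponsor's biostatistics team has been unblinded for the Day 70 analysis (SAP 1.4).

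At Day 70 the issue is narrower. The cut-off is presented as giving everyone two weeks of observation after dose 2, but the actual length depends on when dose 2 was given. Ordinary AEs noted at a Day 70 visit held a few days late are recorded but not tabulated.

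**Working it through.** **1. How late the closing visits can be.** Day 70 visit: 70 + 5 = Day 75. EoS visit: 182 − 14 = Day 168 to 182 + 14 = Day 196. The days beyond the last table are Days 183-196, which is 14 days.

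**2. The plan's own equation.** 56 + 14 = 70, so the gloss on Day 70 is exact for dose 2 on Day 56. For other dosing days, follow-up by Day 70 is 70 minus the dosing day:

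| Dose 2 on | Basis | Days of follow-up by Day 70 | Short of 14 |
|---|---|---|---|
| Day 56 | nominal | 14 | 0 |
| Day 60 | upper end of ±4 (SAP 1.1) | 10 | 4 (29%) |
| Day 61 | upper end of +5 (Protocol) | 9 | 5 (36%) |
| Day 63 | footnote 5, if 7 days run from Day 56 | 7 | 7 (50%) |

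At the lower end of ±4 (Day 52), follow-up would be 70 − 52 = 18 days.

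**3. Where each event goes if the periods are study days.**

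- SAE, MAAE or AESI on Days 71-75: in the Days 71-182 and Days 0-182 tables. Not lost.
- Ordinary unsolicited AE on Days 71-75: in the Days 71-182 listing, in no table. Whether it is collected at all depends on reading Day 70 as the visit, or as dose 2 plus 14 days, rather than as the calendar day.
- SAE on Days 183-196: in no SAP 7.1.2 table or listing. SAP 11.5, which lists all eCRF data, would still show it.
- MAAE or AESI on Days 183-196: the same under Protocol 8.2.2. Under the SAP's own collection text it would not be collected.

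**4. Study days or visit labels?** There is no Day 71 visit, so a period starting at Day 71 reads naturally as study days. SAP 11.5 imputes incomplete AE onset dates relative to the date of the Day 0 vaccination, which is also date-based. No rule assigns events from late visits to a period.

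**5. Expected number of SAEs affected.** Assumptions: 640 participants all followed to EoS, a constant event rate, and EoS visits uniform over Days 168-196. Half the visits then fall after Day 182, by 7 days on average, so the mean excess is 0.5 × 7 = 3.5 days, or 640 × 3.5 = 2,240 person-days. Expected SAEs = 640 × rate × 3.5 / 182.

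- Rate 5% by Day 182 (Protocol 2.1.5.1.1, Phase 2 study in adults 65 and over): 640 × 0.05 × 3.5 / 182 = 0.6.
- Rate 0.8% (Protocol 2.1.5.1.2, Phase 3 study; no day is given, so 182 days is assumed): 640 × 0.008 × 3.5 / 182 = 0.1.
- Extreme case, every EoS visit on Day 196: 640 × rate × 14 / 182 = 2.5 and 0.4.

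**The case against.** The strongest reply is that Day 70 and Day 182 are visit labels. The documents use them that way elsewhere: SAP 1.1 identifies Day 182 with EoS, and Protocol 7.4.1 calls it the last visit. The objective itself is approximate, at about 182 days. On that reading nothing is lost. It is a possible reading, but the Day 71 boundary and the date-based handling in SAP 11.5 point the other way, and the SAP does not state it. SAP 7.1.2 permits summaries for other periods but commits to none.

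A second reply is that the effect is trivial: no safety hypothesis is tested, SAEs are still notified within 24 hours (Protocol 8.3), and the general listings carry them. This stands as to size.

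Three stronger readings are tempting, and the documents do not support them:

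- A reader might infer that SAEs, MAAEs and AESIs are also lost at the Day 70 boundary. They are not; the Days 71-182 tables take them.
- A reader might infer that unsolicited AEs over 14 days after dose 2 are a primary endpoint that the tables fail to deliver. The endpoint runs 70 days from the first dose, and the Days 0-70 table delivers it.
- A reader might infer that the remedy is to extend the unsolicited-AE period to 14 days after the actual second dose and tabulate everything in it. Group O receives a third injection at the Day 70 visit, and its participants and site staff are unblinded from then. The extension would add unblinded post-third-dose events to that reference arm alone. Asking late-dosed participants about the extra days at Day 84 would also change collection, not just wording.

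**Conclusion.** The point holds in a limited form. For SAEs, the collection rule in both documents extends past the last tabulation period. On the natural study-day reading, SAEs on Days 183-196 are left out of every period specified in SAP 7.1.2. For MAAEs and AESIs the same gap exists only under Protocol 8.2.2, because SAP 7.1.2 and Protocol 9.3.6.2 end collection at Day 182; that disagreement needs resolving in its own right. At Day 70, the stated equivalence with two weeks after dose 2 fails for any dose not given on Day 56, and ordinary AEs recorded at a late Day 70 visit have a listing but no table.

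The size is small: about 0.1 to 0.6 SAEs over the whole trial under the assumptions in step 5, and at most about 2.5 in the extreme case. No safety conclusion is likely to turn on it. It is still worth correcting, because it touches primary safety endpoints and the correction costs very little.

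**What to change.** (a) In SAP 7.1.2 and Protocol 9.3.1 and 9.3.6.2, end the last SAE, MAAE and AESI period at each participant's actual EoS visit (Days 71-EoS and Days 0-EoS), in tables and listings. Reconcile the collection wording for MAAEs and AESIs in SAP 7.1.2 and Protocol 9.3.6.2 with Protocol 8.2.2.

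(b) Keep the Days 0-70 table, since it matches the stated endpoint. Add a table of unsolicited AEs already recorded through the actual Day 70 visit, with Group O events after its third dose excluded or shown separately.

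(c) Reconcile the statement that Day 70 is 14 days after dose 2 with the dose 2 window, and reconcile the two versions of that window (+5 days in the Protocol and both schedules of events, ±4 days in SAP 1.1 and SAP Table 1).

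Cost: wording in both documents, date derivations and one extra table; no new data collection. Downside: follow-up length will vary slightly with visit date, and event counts may rise slightly.
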